2 STUDY OBJECTIVES

2.1 Objectives

2.1.1 *Primary objective*

Primary objective of the study is to investigate the effect of food on the bioavailability of DF 2156Y after single dose administration of 400 mg of ladarixin to healthy male and female volunteers under fed and fasting conditions.

2.1.2 *Secondary objectives*

- to investigate the effect of gender on the bioavailability of DF 2156Y and its metabolites (DF 2108Y and DF 2227Y) after single dose administration of 400 mg of ladarixin to healthy male and female volunteers;
- To evaluate safety and tolerability of a single dose administration of 400 mg ladarixin to healthy male and female volunteers.

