2.2 Endpoints

2.2.1 *Primary end-point*

- to evaluate and compare the rate (C_{max}) and extent (AUC_{0-t} ; $AUC_{0-\infty}$) of absorption of DF 2156Y after single dose administration of 400 mg of ladarixin under fed and fasting conditions.

2.2.2 *Secondary end-points*

- to evaluate and compare between genders the rate (C_{max}) and extent (AUC_{0-t} ; $AUC_{0-\infty}$) of absorption of DF 2156Y and its metabolites (DF 2108Y and DF 2227Y) after single dose administration of 400 mg of ladarixin to healthy male and female volunteers;
- to describe the pharmacokinetic profile of DF 2156Y (total and unbound) and its metabolites (DF 2108Y and DF 2227Y) after single dose administration of 400 mg of ladarixin under fed and fasting conditions;
- to collect safety and tolerability data of a single oral dose administration of 400 mg of ladarixin.

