3 CLINICAL SUPPLIES

3.1 Treatment

3.1.1 *Description of product*

The analytical certificate will be supplied with the investigational medicinal product (IMP).

3.1.1.1 *Test product*

IMP	Ladarixin 200 mg hard gelatin capsules
Distributor	Dompé farmaceutici S.p.A., Italy
Manufacturer (active substance)	AMSA S.p.A, Como, Italy
Manufacturer (finished product)	Depo Pack s.n.c., Saronno (Va), Italy
Pharmaceutical form	Hard gelatin capsules
Dose	400 mg (two 200 mg capsules)
Administration route	Oral

3.1.2 *Dose regimen*

A single oral dose of 400 mg of ladarixin (two 200-mg capsules) will be administered to healthy male and female volunteers under fed (T treatment) and fasting (R treatment) conditions in 2 study periods, according to a two-way crossover design, with a wash-out interval of at least 14 days between the two administrations.

3.1.3 *Route and method of administration*

The IMP will be orally administered on day 1 of each period, at $8:00 \pm 1$ h. In detail, at each dosing, 2 capsules will be swallowed with 240 mL of still mineral water, without chewing.

The subjects allocated to the fed conditions will receive the IMP 30 min after having started to eat a high-fat and high-caloric breakfast (§ 6.2.1), while the subjects allocated to the fasting conditions will receive the IMP under prolonged fasting conditions (at least 10 h pre-dose).

The investigator will check that all subjects take the IMP appropriately.

3.1.4 *Investigational product distribution*

The IMP will be administered by the investigator or by his/her deputy at the Phase I Unit. The IMP will be exclusively used for the present clinical study and will only be administered to the subjects enrolled in the study.

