5.2 Inclusion criteria

To be enrolled in this study, subjects must fulfill all these criteria:

1. *Informed consent*: signed written informed consent before inclusion in the study
2. *Sex and Age*: men/women, 18-55 years old inclusive
3. *Body Mass Index (BMI)*: 18.5-30 kg/m² inclusive
4. *Vital signs*: systolic blood pressure (SBP) 100-139 mmHg, diastolic blood pressure (DBP) 50-89 mmHg, pulse rate (PR) 50-90 bpm and body temperature (BT) 35.5-37.5° C, measured after 5 min at rest in the sitting position
5. *Full comprehension*: ability to comprehend the full nature and purpose of the study, including possible risks and side effects; ability to co-operate with the investigator and to comply with the requirements of the entire study
6. *Contraception and fertility (women only)*: women of child-bearing potential must not wish to get pregnant within 30 days after the end of the study and must be using at least one of the following reliable methods of contraception:
 - a. Hormonal oral, implantable, transdermal, or injectable contraceptives for at least 2 months before the screening visit until 30 days after final visit
 - b. A non-hormonal intrauterine device [IUD] or female condom with spermicide or contraceptive sponge with spermicide or diaphragm with spermicide or cervical cap with spermicide for at least 2 months before the screening visit until 30 days after final visit
 - c. A male sexual partner who agrees to use a male condom with spermicide until 30 days after final visit
 - d. A sterile sexual partner

Women participants of non-childbearing potential or in post-menopausal status for at least one year will be admitted.

For all women, pregnancy test result must be negative at screening and day -1.

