7 DESCRIPTION OF SPECIFIC PROCEDURES

7.1 Physical examination

Full physical examinations will be performed at:

- screening visit
- on day 4 of period 1 (before discharge)
- on day -1 of period 2
- final visit/ETV.

Body weight will be recorded each time. Subjects will be weighed (kg) lightly clothed without shoes. Height will be measured at screening only and BMI will be recorded. BMI will be calculated as weight [kg]/(height [m] x height [m]).

Information about the physical examination will be recorded by the investigator. Any abnormalities will be recorded.

Significant findings/illnesses, reported after the start of the study and that meet the definition of an AE (see § 11), will be recorded in the subject source documents.

Date of the physical examination, overall investigator's interpretation (as normal or abnormal and, if abnormal, clinically significant or not clinically significant) and clinically significant abnormalities (if any) will be reported in the individual electronic case report forms (eCRF).

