10.4 Analysis of pharmacokinetic parameters

10.4.1 Descriptive pharmacokinetics

A descriptive PK will be presented for plasma total and unbound DF 2156Y and its metabolites DF 2108Y and DF 2227Y. The results will be displayed and summarized in tables and figures. Individual and mean curves (+SD at sampling times), indicating inter-subject variability, will be plotted. Mean curves will be presented by treatment and by treatment and sex.

PK parameters of total plasma DF 2156Y and its metabolites DF 2108Y and DF 2227Y will be summarized by treatment and by treatment and sex.

Data below the lower quantification limit (BLQL) will be considered as 0 in the calculations and presented as BLQL in listings and tables. As a consequence of BLQL (i.e. 0) values, calculated geometric means (if requested) could be null. For this reason, in the presence of any null value, the geometric mean will be reported as NC. If for an individual PK curve, a log-linear regression with a correlation coefficient $R^2 > 0.8$ cannot be obtained, the extrapolated PK parameters will be reported as NC and considered missing in the calculations of descriptive statistics.

10.4.2 *Statistical comparison of pharmacokinetic parameters*

For the primary end-point evaluation of food effect, C_{max} , AUC_{0-t} and $AUC_{0-\infty}$ of total plasma DF 2156Y will be compared between fed and fasting conditions (T vs. R) using analysis of variance (ANOVA) for a cross-over design on log-transformed data for evaluation of the food effect. Period, treatment, sequence and subject within sequence will be taken in account as sources of variation and they will be treated as fixed effect.

The 90% confidence intervals (CI) will be calculated for the point estimates (PE, i.e. the T/R ratio of least square geometric means) of the PK parameters.

Established criteria for the absence of a food effect are that the 90% CI for the T/R ratio of the geometric means of the PK parameters under consideration are within the 80.00-125.00% range.

For the purpose of exploring the gender effect on bioavailability of ladarixin and its metabolites, following logarithmic transformation, C_{max} , AUC_{0-t} and $AUC_{0-\infty}$ of total plasma DF 2156Y and of DF 2108Y and DF 2227Y will be analyzed using ANOVA including sequence, period, treatment, subject within sequence, sex and sex*treatment interaction as fixed effect.

10.5 *Safety and tolerability evaluation*

➤ AEs

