AEs will be coded by System Organ Class (SOC) and Preferred Term (PT), using the Medical Dictionary for Regulatory Activities (MedDRA).

AEs will be classified as pre-treatment AEs (PTAEs) and TEAEs, according to the period of occurrence, as follows:

- PTAEs: all AEs occurring after informed consent signature by the enrolled subject but before the first dose of IMP and not negatively affected by the first dose of IMP;
- TEAEs: all AEs occurring or worsening after the administration of the first dose of IMP.

Individual PTAEs and TEAEs will be listed in subject data listings. No summary table will be provided for PTAEs. TEAEs will be summarized by treatment and overall. The number and percentage of subjects with any TEAE and the number of TEAEs will be tabulated by SOC and PT, seriousness, relationship to treatment and severity.

➤ Physical examination

Date of the physical examination, overall investigator's interpretation (as normal or abnormal and, if abnormal, clinically significant or not clinically significant) and clinically significant abnormalities (if any) will be listed.

➤ Laboratory data

Date/time of samples collection, overall investigator's interpretation (as normal or abnormal and, if abnormal, clinically significant or not clinically significant) and all abnormalities found (if any) will be listed. All laboratory results will be listed and a table of all the abnormal values will be presented. The overall investigator's interpretation will be summarized using tables of frequency.

➤ Vital signs

Vital signs values will be listed and summarized by descriptive statistics.

➤ Body weight

Body weight values will be listed and summarized by descriptive statistics.

➤ ECG

Date/time of ECG recording, overall investigator's interpretation (as normal or abnormal and, if abnormal, clinically significant or not clinically significant) and all abnormalities found (if any) will be listed. The overall investigator's interpretation will be summarized using tables of frequency

11 DEFINITION AND HANDLING OF AEs AND SAEs

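### The exploratory between-sex comparison at a flat 400 mg dose omits recorded body weight, so it cannot tell sex from body size, and the stated model has no room for weight

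*Protocol*

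**What the plan says.** Protocol section 2.1.2 sets a secondary objective "to investigate the effect of gender on the bioavailability of DF 2156Y and its metabolites (DF 2108Y and DF 2227Y"), and section 2.2.2 adds an end-point "to evaluate and compare between genders the rate" and extent of absorption (Cmax, AUC0-t, AUC0-inf).

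The dose is the same for all. Section 3.1.2: "A single oral dose of 400 mg of ladarixin (two 200-mg capsules) will be administered to healthy male and female volunteers".

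Section 10.4.2, repeated in the synopsis, opens the analysis with "For the purpose of exploring the gender effect on bioavailability of ladarixin and its metabolites" and says that the log-transformed parameters "will be analyzed using ANOVA including sequence, period, treatment, subject within sequence, sex and sex*treatment interaction as fixed effect". No weight term, per-kilogram normalisation or weight-adjusted result appears.

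Section 7.1 schedules physical examinations at screening, day 4 of period 1, day -1 of period 2 and the final visit, and states "Body weight will be recorded each time". The only planned use is in the safety section, 10.5: "Body weight values will be listed and summarized by descriptive statistics". Body size at entry is limited only through BMI (section 5.2, "18.5-30 kg/m² inclusive"). Stratification by sex (section 8.1) balances sex over sequences, not weight between the sexes.

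**The concern.** If men and women in the trial differ in weight and exposure depends on weight, a flat dose produces a sex difference in Cmax and AUC even when sex itself has no effect. The objective is worded as an effect of gender on bioavailability, and section 1.5 says that PK has so far been studied only in men. A reader of the report will therefore want to know whether any difference in women is more than a difference in size. The planned output contains nothing that addresses this, although the needed variable is already collected.

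The obvious repair, adding weight to the list of terms, also fails for a structural reason: the stated model absorbs everything that is constant within a subject.

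**Working it through.** The protocol gives no figure for the between-sex comparison, so there is none to reproduce. Three checks follow.

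**1. What the stated model can estimate.** Design matrix for 36 subjects and two periods (72 observations):

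- intercept, sequence, period, treatment and subject within sequence, all fixed: rank 38 (36 for subjects, 1 for period, 1 for treatment)
- adding sex: rank 38
- adding sex-by-treatment: rank 39
- adding log screening weight: rank 39

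Sex and screening weight are both constant within a subject, so the subject columns already contain them. The only estimable sex term that the model adds is sex-by-treatment, a within-subject contrast from which weight cancels. A between-sex ratio must come from the by-sex summaries or from a between-subject error term that section 10.4.2 does not name.

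**2. Possible size of the body-size part.** Assumptions, not in the documents: male/female mean weight ratio 1.1 to 1.3, and AUC proportional to weight^-0.75. Female/male AUC ratio from size alone = (weight ratio)^0.75:

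| Weight ratio | AUC ratio |
|---|---|
| 1.1 | 1.074 |
| 1.2 | 1.147 |
| 1.3 | 1.217 |

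An exponent of 1 would give 1.10 to 1.30. An exponent of 0 would give no contribution.

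For scale, compare the precision of the sex ratio:

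- AUC0-inf at 400 mg in men, Tables 1.4.2.1 and 1.4.3.1: CV = 159.99/921.54 = 17.4% and 188.0/1063.2 = 17.7%. SD(log) = sqrt(ln(1+CV²)) = 0.172 and 0.176; 0.174 is used, and women are assumed to vary alike.
- With the synopsis minimum of 16 completers per sex: SE = 0.174 × sqrt(2/16) = 0.0615.
- 90% CI half-width = 1.697 × 0.0615 = 0.104 on the log scale, a factor of 1.11.

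Under these assumptions the size contribution runs from somewhat below the half-width to about twice it.

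**3. Does adjustment separate the two?** Simulation, 4000 runs, 18 per sex, assumed typical weights of 75 and 62 kg, exposure proportional to weight^-1, no true sex effect, analysis of subject means:

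- female/male ratio without weight: 1.21 (as expected, 75/62 = 1.21)
- with log weight as covariate: 1.00
- sex-by-treatment ratio without weight: 1.00

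The cost is collinearity. For a sex-weight correlation r, the SE is multiplied by 1/sqrt(1-r²): 1.15 at r = 0.5 and 1.40 at r = 0.7 (assumed values). The half-width factor becomes exp(1.699 × 0.0615 × 1.155) = 1.13 to exp(1.699 × 0.0615 × 1.400) = 1.16, before any gain from variance that weight explains.

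**The case against.** The strongest reply is that the unadjusted contrast answers the question asked. The end-point compares Cmax and AUC between the sexes after 400 mg, the protocol uses bioavailability to mean those quantities, and weight may be part of how sex affects exposure rather than a nuisance. This stands: the unadjusted ratio is legitimate and should stay. It does not follow that it is enough on its own.

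A second reply is that a supplementary adjusted analysis is ordinary SAP content, and an SAP not seen here may contain one. That is possible. But the protocol fixes the term list itself, and a weight covariate placed in that list could not work. The form of the between-sex model therefore needs correcting where it is stated.

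Three stronger readings are tempting, and the documents do not support them:

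- A reader might infer that the trial is likely to declare a false gender effect. No sex test, significance level or decision rule is planned. Section 10.4.2 calls the analysis exploratory, and the 90% CI with the 80.00-125.00% range is stated for fed versus fasting only.
- A reader might infer that the food-effect result is contaminated. It is within-subject, as are F_rel and sex-by-treatment.
- A reader might take the 7 to 22% as a property of ladarixin. The documents give neither weights by sex nor a weight-exposure relation.

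It is also true that individual weights will be listed, so an adjusted analysis could be done afterwards. It would then be post hoc.

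**Conclusion.** The point holds in limited form. For the secondary objective on gender, the plan can describe a total exposure difference at a flat dose but cannot attribute it to sex rather than body size. As written, the model does not estimate a sex main effect at all. The rank result follows from the stated design and needs no assumption. The size of the body-size contribution, about 7 to 22% in AUC, rests wholly on the assumed weight ratios and the exponent of 0.75. The primary analysis is untouched. This is a modest improvement to an exploratory secondary analysis, worth making because it needs no new data.

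**What to change.** In section 10.4.2 and the synopsis, for the exploratory between-sex comparison only:

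- Replace the all-fixed model with one that keeps sequence, period, treatment, sex and sex-by-treatment fixed and takes subject as a random effect. An equivalent choice is to analyse each subject's mean log value over the two periods.
- Report the female/male ratio with its 90% CI for Cmax, AUC0-t and AUC0-inf of DF 2156Y, DF 2108Y and DF 2227Y, unadjusted and adjusted for log screening body weight, side by side.
- State that the unadjusted ratio describes the exposure difference at 400 mg and the adjusted ratio the difference at equal weight.

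The food-effect ANOVA stays as it is. The cost is one extra model per parameter (three parameters × three analytes = nine) and an adjusted interval that may be wider: SE about 15 to 40% higher at an assumed sex-weight correlation of 0.5 to 0.7, before any gain from variance explained by weight. With 16 to 18 subjects per sex the adjusted ratio may be inconclusive, which is a further reason to show both.

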Safety and tolerability assessments: Treatment-emergent adverse events; vital signs (blood pressure, pulse rate, body temperature), physical examinations including body weight; laboratory tests (hematology, blood chemistry and urine analysis), electrocardiograms

Sample size: The sample size was not calculated through any statistical calculation. In order to have at least 32 subjects completed (16 men and 16 women), a sample size of 36 healthy volunteers (18 men and 18 women) was estimated as sufficient for the descriptive purposes of the present study. Drop-out subjects will be replaced starting from the 3rd man and/or woman discontinuing prematurely the study.

Main selection criteria:

Inclusion criteria:

1. *Informed consent*: signed written informed consent before inclusion in the study
2. *Sex and Age*: men/women, 18-55 years old inclusive
3. *Body Mass Index*: 18.5-30 kg/m² inclusive
4. *Vital signs*: systolic blood pressure 100-139 mmHg, diastolic blood pressure 50-89 mmHg, pulse rate 50-90 bpm and body temperature 35.5-37.5° C, measured after 5 min at rest in the sitting position
5. *Full comprehension*: ability to comprehend the full nature and purpose of the study, including possible risks and side effects; ability to co-operate with the investigator and to comply with the requirements of the entire study
6. *Contraception and fertility (women only)*: women of child-bearing potential must not wish to get pregnant within 30 days after the end of the study and must be using at least one of the following reliable methods of contraception:
 - a) Hormonal oral, implantable, transdermal, or injectable contraceptives for at least 2 months before the screening visit until 30 days after final visit
 - b) A non-hormonal intrauterine device or female condom with spermicide or contraceptive sponge with spermicide or diaphragm with spermicide or cervical cap with spermicide for at least 2 months before the screening visit until 30 days after final visit
 - c) A male sexual partner who agrees to use a male condom with spermicide until 30 days after final visit
 - d) A sterile sexual partner

Women participants of non-childbearing potential or in post-menopausal status for at least one year will be admitted. For all women, pregnancy test result must be negative at screening and day -1.

Exclusion criteria:

1. *Electrocardiogram (ECG) 12-leads (supine position)*: clinically significant abnormalities

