The pharmacokinetic analysis and the statistical analysis of pharmacokinetic parameters will be performed using Phoenix WinNonlin® version 6.3 or higher, Pharsight Corporation, and SAS® version 9.3 (TS1M1) or higher. The statistical analysis of safety and tolerability data will be performed using SAS® version 9.3 (TS1M1) or higher. The data documented in this trial and the clinical parameters measured will be analyzed using classic descriptive statistics for quantitative variables and frequencies for qualitative variables.

Analysis of primary end-point

For the evaluation of food effect, C_{max} , AUC_{0-t} and $AUC_{0-\infty}$ of total plasma DF 2156Y will be compared between treatments using analysis of variance (ANOVA) for a crossover design on log-transformed data. Period, treatment, sequence and subject within sequence will be taken into account as sources of variation. The 90% confidence intervals (CI) will be calculated for the point estimates (PE, i.e. the T/R ratio of least square geometric means) of the PK parameters. Established criteria for the absence of a food effect are that the 90% CI for the T/R ratio of the geometric means of the PK parameters under consideration are within the 80.00-125.00% range

Gender effect analysis

For the purpose of exploring the gender effect on bioavailability of ladarixin and its metabolites, following logarithmic transformation, C_{max} , AUC_{0-t} and $AUC_{0-\infty}$ of total plasma DF 2156Y and of DF 2108Y and DF 2227Y will be analyzed using ANOVA including sequence, period, treatment, subject within sequence, sex and sex*treatment interaction as fixed effect.

Timing:

EC meeting: 16JUN20; planned clinical phase: NOV20

STUDY SCHEDULE

ACTIVITIES	Screening		PERIOD 1			(wash-out \geq 14 days)	PERIOD 2			Final visit/ETV ¹	
	Visit	V1	V1.1	V2	V3		V4	V5	V6		
		Day - 21/-2	Day -3 or -2	Day -1	Day 1	Days 2, 3, 4					
Informed consent	x										
Demography	x										
Lifestyle	x										
Medical history and underlying disease	x										
Physical abnormalities	x					x ³		x		x	
Previous and concomitant medications	x	x	x	x	x	x	x	x	x	x	
Height and Body Mass Index	x										
Body Weight	x					x ³		x		x	
Laboratory analysis⁴	x									x	
Virology	x										
SARS-COV2 test		x					x				
Pregnancy test	x ⁵		x ⁶					x ⁶		x ⁵	
Urine drug screening⁷	x		x					x		x	
Alcohol breath test	x		x					x		x	
Coagulation	x										
Vital signs¹⁰	x		x	x ⁸	x ⁹		x	x ⁸	x ⁹	x ¹¹	
ECG	x		x	x ⁸	x ⁹		x	x ⁸	x ⁹	x ¹¹	

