10 STATISTICAL METHODS

The data documented in this study and the parameters measured will be evaluated and compared using classic descriptive statistics, i.e. geometric mean (PK data only), arithmetic mean, standard deviation (SD), coefficient of variation (CV) %, minimum, median and maximum values for quantitative variables, and frequencies for qualitative variables.

Not available data will be evaluated as “missing values”. The statistical analysis of demographic and safety data will be performed using SAS® version 9.3 (TS1M1) (12) or higher (the actual version will be stated in the final report).

The statistical analysis of PK parameters will be performed using Phoenix WinNonlin® version 6.3 (13) or higher and SAS® version 9.3 (TS1M1) or higher.

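### The gender-effect ANOVA fits every subject and sex as fixed effects, so sex has 0 df and the model gives no female/male estimate or test

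*Protocol*

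**What the plan says.** Section 10.4.2 of the protocol introduces the model "For the purpose of exploring the gender effect on bioavailability of ladarixin and its metabolites". After log transformation, three parameters for each of three analytes "will be analyzed using ANOVA including sequence, period, treatment, subject within sequence, sex and sex*treatment interaction as fixed effect". The synopsis (Data analysis, Gender effect analysis) repeats the term list: "ANOVA including sequence, period, treatment, subject within sequence, sex and sex*treatment interaction as fixed effect". Neither place mentions a random subject term, nesting of subject in sex, or a separate error term for sex.

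The model serves a secondary objective (section 2.1.2) and a secondary end-point (section 2.2.2), which is "to evaluate and compare between genders the rate" and extent of absorption of the parent and its metabolites. Section 8.1 stratifies randomization by sex so that each sequence has equal numbers of men and women.

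There is also a descriptive route. Section 10 says the data "will be evaluated and compared using classic descriptive statistics", and section 10.4.1 says the PK parameters "will be summarized by treatment and by treatment and sex".

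**The concern.** Sex is a between-subject factor. A model with a separate fixed intercept for every subject has already used up all between-subject differences, including the difference between women and men. The model is written to explore that difference, yet nothing is left from which to estimate it.

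Sequence is aliased with subject in the same way, and that is harmless because no end-point asks for a sequence estimate. Here the lost term is the target. What remains, sex by treatment, asks whether the food effect differs between the sexes. It does not ask whether exposure differs between women and men, which is what the end-point asks.

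If the protocol is programmed literally, the output for sex will be blank or flagged as non-estimable. The programmer may then improvise a workaround that the protocol does not specify.

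**Working it through.** The protocol gives no df, power or calculated sample size for this analysis, so there is no figure to reproduce. The check uses the design alone and assumes no variance.

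**Inputs**
- 36 subjects, 18 men and 18 women (section 10.2). With stratification by sex this gives 9 per sex per sequence.
- 32 completers, 16 men and 16 women (synopsis, Sample size), or 8 per sex per sequence.
- Two periods per subject, sequences TR and RT (section 4.2), hence 36 × 2 = 72 or 32 × 2 = 64 observations.
- Model terms as listed in section 10.4.2, all fixed.

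**Why sex is aliased.** Let S_i be the indicator column for subject i. The indicator for women is the sum of S_i over all women, exactly. Any model containing every S_i already contains it. This holds at any sample size and under any imbalance or dropout pattern; an unbalanced 17 + 16 design also gave sex 0 df.

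**Degrees of freedom**, taken as the rise in the rank of the design matrix as each term enters in the listed order:

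| Term | 36 subjects | 32 subjects |
|---|---|---|
| Intercept | 1 | 1 |
| Sequence | 1 | 1 |
| Period | 1 | 1 |
| Treatment | 1 | 1 |
| Subject within sequence | 34 | 30 |
| *Rank before sex* | *38* | *34* |
| Sex | **0** | **0** |
| *Rank after sex* | *38* | *34* |
| Sex × treatment | 1 | 1 |
| *Final rank* | *39* | *35* |
| Residual | 72 − 39 = 33 | 64 − 35 = 29 |

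**Estimability.** A contrast is estimable only if it lies in the row space of the design matrix. The female-minus-male least-squares mean contrast fails this check averaged over treatments, within fed and within fasting. The sex-by-treatment contrast passes.

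**With subject as the between-subject error stratum.** Between-subject df are N minus 3 (intercept, sequence, sex): 36 − 3 = 33 or 32 − 3 = 29. Sex then has 1 df and is tested as F(1, 33) or F(1, 29).

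**If sex is tested against the wrong error.** Suppose sex is entered before subject and tested against the residual. With complete pairs, the expected mean square for sex under no sex effect is σ²w + 2σ²b, while the residual estimates σ²w. The F statistic is inflated by 1 + 2r, where r = σ²b/σ²w. The documents do not give r, so the range 0.5 to 4 is an assumption. At 36 subjects the 5% critical value of F(1, 33) is 4.14:
- r = 0.5: inflation 2, and P(F(1, 33) > 4.14/2) is about 16%.
- r = 4: inflation 9, and P(F(1, 33) > 4.14/9) is about 50%.

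A nominal 5% test would reject falsely about 16% to 50% of the time over that range.

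**The case against.** The strongest reply is that this is loose notation. Listing a between-subject factor beside subject within sequence, and testing it against the subject mean square, is ordinary crossover ANOVA, and the protocol does not fix the order of entry or the type of sum of squares. If sex enters before subject it gets 1 df, subject 33, the interaction 1 and the residual 33. A contrast that averages over each sex's own subjects is estimable even in the fixed-effects matrix. On this view, nesting and error term are details for the analysis plan, which is not shown.

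The algebra in that reply is correct, but none of those readings is written down. The protocol names every term, calls them all fixed, nests subject in sequence only, and does so in two places. Entering sex first, or using the own-subjects contrast, leaves the within-subject residual as the default error, which is wrong for sex. Testing against the subject mean square is right, but it is the repair and not what the protocol states. An analysis plan that follows the protocol inherits the defect; one that corrects it departs from the protocol and should say so.

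The reply is right about consequence. The analysis is exploratory, and no alpha, confidence interval or acceptance range is set for sex. The by-sex tables and curves still give a descriptive comparison, and the interaction is intact. It is also fair that the PK-set definitions in section 10.1.1, which require compliance with treatment intake, can be read as requiring both periods. Gaps in the data are certain to be possible only for extrapolated parameters, which section 10.4.1 allows to be reported as not calculated.

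**Conclusion.** The point holds. As written, the only model the protocol names for the between-gender end-point has 0 df for sex and cannot return a female/male estimate or test. This affects all 9 parameter-by-analyte models at 36 subjects, at 32 completers and at any other number. The result rests on sex being constant within a subject and on the terms being fixed as stated; it needs no variance assumption. The false-positive range for the improvised test does rest on assumed variance ratios and is illustrative only.

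The damage is limited to the inferential part of an exploratory secondary analysis. The descriptive by-sex comparison, the sex-by-treatment interaction and the primary food-effect ANOVA all stand. It should be fixed, because the model cannot answer its own question and the correction costs almost nothing.

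**What to change.** In the gender model only, make subject, nested in sequence and sex, a random effect, and keep sequence, period, treatment, sex and sex by treatment fixed. Report the female/male geometric mean ratio with a confidence interval based on between-subject error, and test the interaction against the within-subject residual.

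With complete pairs this is equivalent to an ANOVA that tests sex against the between-subject mean square (33 df at 36 subjects, 29 at 32). A check on simulated data gave the same sex estimate and standard error both ways. When 4 subjects contributed one period only, the two differed, so the plan should name one method.

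Leave the primary food-effect ANOVA as it is. The note to file of 19 January 2021 records that the clinical phase is over, so the change belongs in the analysis plan and the study report. The cost is one sentence and one changed procedure call or named error term, with no new data or subjects and no change to the descriptive tables.
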